3.1 Inclusion Criteria

Unless otherwise specified, the following are required at enrollment:

- A. Prostate cancer patients with a PSA after prostatectomy of at least 0.1 ng/mL and up to 4.0 ng/mL within 3 months prior to enrollment.
- B. Patients with or without palpable abnormalities on digital rectal exam (DRE) are eligible.
- C. Minimum of 3 months since prostatectomy to allow for return of urinary continence and healing.
- D. Imaging detectable lesion or lesions in prostate bed or regional LN. Each lesion should be at least 0.4 cc and a maximum of 6 cc and was obtained \leq 3 months prior to protocol entry or enrollment.
- E. No evidence of metastatic (distant) disease (pelvic nodes are allowed up to common iliac).
- F. Negative bone scan if deemed necessary by treating physician obtained \leq 4 months prior to protocol entry or enrollment..
- G. No previous pelvic radiotherapy.
- H. Serum total testosterone taken within 3 months prior to enrollment.
- I. No concurrent, active malignancy, other than nonmetastatic skin cancer or early stage chronic lymphocytic leukemia (well-differentiated small cell lymphocytic lymphoma). If a prior malignancy is in remission for \geq 3 years then the patient is eligible.
- J. Ability to understand and the willingness to sign a written informed consent document.
- K. Zubrod performance status <2.
- L. Patients must agree to fill out quality of life/psychosocial questionnaires.

M. Age ≥ 35 and ≤ 85 years.

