9.1 Definitions

- *PSA response rate*: The proportion of study patients with PSA <0.1 ng/mL at 21 months after completion of study treatment.
- *Acute toxicity*: Toxicity occurring during treatment and within three months of completing treatment.
- *Late toxicity*: Toxicity occurring more than three months after treatment completion. *Failure rate*: The cumulative incidence of biochemical or clinical failure allowing for competing risk as needed. Clinical failure is defined as at least a 25% increase in the size of the tumor relative to the smallest volume recorded, or new extension of tumor beyond the capsule, or re-extension of tumor beyond the capsule after initial regression, or urinary obstructive symptoms with carcinoma found at TURP. Biochemical failure is defined as PSA \geq nadir + 2 ng/mL.

- *Failure-free Survival (FFS)*: The elapsed time from start of radiotherapy to first documented evidence of biochemical or clinical failure or death from any cause, whichever occurs first. In the absence of any event defining failure, follow-up time will be censored at the date of last documented failure-free status.
- *Overall Survival (OS)*: The elapsed time from start of radiotherapy to death from any cause. For surviving patients, follow-up will be censored at the date of last contact.
- *Biomarker expression*: Quantification of the amount of the biomarker specific immunohistochemical staining in the area of tumor.
- *QOL*: Two contemporary instruments will be utilized to assess patient function and bother (Expanded Prostate Cancer Index Composite-SF12 (EPIC-SF12) and prostate cancer-specific anxiety Memorial Anxiety Scale for Prostate Cancer patients (MAX-PC).

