9.2 Guidelines for Evaluation of Measurable Disease

9.2.1 Clinical primary tumor response will be measured by palpation and recorded in the following ways:

- Pretreatment: A representative drawing of the pretreatment tumor status on DRE, if palpable, will be recorded in the radiotherapy chart.
- Post-treatment: The change in palpable tumor volume will be recorded qualitatively.

9.2.2 PSA levels:

In 98% of patients treated with salvage radiotherapy there is a drop in PSA within 3 months. Those patients that PSA levels have not dropped should be investigated to define the site of progression (local-regional vs. distant metastases). In the rest of the patients, a rising PSA later heralds relapse. Biochemical failure will be modeled after the Nadir+2 definition.[49] Evaluation of patients with a rising PSA profile will include a bone scan, MRI-pelvis/prostate bed, and prostate bed biopsy.

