Evaluable: Patients who are study eligible and receive an initial dose of *MTSRT* will be considered *evaluable for safety*, regardless of whether or not the full course of radiation treatment is completed according to protocol. To be *evaluable for efficacy*, study eligible patients must either (1) complete radiation treatment and the nine month post treatment PSA assessment or (2) initiate therapy but develop evidence of biochemical or clinical failure, or die from causes related to prostate cancer, within nine months of stopping or completing treatment. In the latter case (2), which is expected to be rare, patients will be included as non-responders in the evaluation of PSA response rate. The set of patients who are evaluable for efficacy comprise the main analysis set.

Exclusions: Any patient who is enrolled on study but does not receive an initial dose of radiation treatment will be excluded from all efficacy analyses. Any patient who initiates treatment and is later found to be ineligible for study (e.g., protocol violation) will be withdrawn from study but will be followed for toxicity and clinical outcome; the experience of such patients will be characterized separately from that of patients who are evaluable for efficacy. Reasons for exclusion of enrolled patients from analysis of safety or efficacy will be characterized.

Study endpoints are defined in **Section 9.1**.

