The primary trial endpoint, *PSA response rate*, will be estimated as a proportion with corresponding 95% confidence interval by the exact binomial method. Biomarker and proteomic/genomic characteristics of baseline prostate bed biopsy tissue will be summarized by descriptive statistics. Additionally, biomarker and proteomic/genomic characteristics measured in blood samples obtained at baseline, RT completion, and 3 months post RT will also be studied and changes from baseline will be tested for significance using t-test (means) or McNemar's test (proportions) for paired data. (For biomarker studies, nonparametric tests or data transformations to attain approximate normal distributions will be applied as needed.) Logistic regression models will be used to investigate the association between baseline factors, including biomarkers and proteomic/genomic profiles, and PSA response. Changes in biomarkers and proteomic/genomic characteristics measured in blood will also be investigated for association with PSA response.[52]

Patients will be followed for disease progression and vital status for a period of five years after completing study treatment. Progression of disease will be categorized as biochemical failure (BF), clinical failure (CF), or combined (BF + CF), where combined failure refers to documented evidence of BF and CF occurring within 6 months of each other with the earlier date used. CFs will be further categorized as local, nodal, or distant. Start of subsequent therapy will be considered a failure event for selected analyses as indicated in the table below. Deaths will be categorized as related/unrelated to prostate cancer. The number of observed failures will be tabulated by failure type. Similarly, vital status will be tabulated by presence or absence of disease at last follow-up.

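### Clinical failure in section 9.1 uses criteria for an intact prostate, names no nodal or distant event, and conflicts with section 14.5

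*Combined protocol and SAP*

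**What the plan says.** The population is defined in section 3.1: "Prostate cancer patients with a PSA after prostatectomy of at least 0.1 ng/mL and up to 4.0 ng/mL". Lesions may lie in the prostate bed or regional nodes, and a palpable abnormality is not required.

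Section 9.1 gives four alternative criteria for clinical failure:

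- Size: "Clinical failure is defined as at least a 25% increase in the size of the tumor relative to the smallest volume recorded".
- Capsule, two criteria: "new extension of tumor beyond the capsule, or re-extension of tumor beyond the capsule after initial regression".
- TURP: "urinary obstructive symptoms with carcinoma found at TURP".

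Biochemical failure is a PSA of nadir + 2 ng/mL or more.

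Section 9.2.1 measures local tumor response by palpation. After treatment, "The change in palpable tumor volume will be recorded qualitatively". Sections 9.2.3 and 9.2.4 say when nodal and hematogenous relapse are scored, but do not call either one clinical failure.

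Section 14.5 says "CFs will be further categorized as local, nodal, or distant". Section 14.3 refers the reader to 9.1 for the endpoint definitions.

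Clinical failure also enters the efficacy set in section 14.3. Route (1) is completed radiotherapy plus the nine-month PSA. Route (2) is for men who "initiate therapy but develop evidence of biochemical or clinical failure, or die from causes related to prostate cancer"; the event must fall in the nine months after radiotherapy ends, whether or not the course was finished. Route (2) men count as non-responders and are expected to be rare.

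**The concern.** An endpoint definition should let two people classify the same patient in the same way. Here they may not. One who follows 9.1, as 14.3 directs, has no criterion under which a new pelvic node or bone lesion is a clinical failure. One who follows 14.5 counts both. For local progression, neither is told which measurement the 25% rule applies to.

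Clinical failure feeds the failure rate, failure-free survival and route (2) of the primary analysis set. For the first two, the risk is a missed event or a late event date. For the third, the risk is that a treatment failure leaves the denominator, which raises the observed response rate. If the choice between readings is left until outcomes are known, it becomes data-dependent.

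**Working it through.** **Step 1. Do the 9.1 criteria fit the population?**

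| Criterion in 9.1 | Usable after prostatectomy? |
|---|---|
| Size increase of at least 25% over the smallest volume | Yes, if a volume is measured |
| New extension beyond the capsule | No; the gland and its capsule have been removed |
| Re-extension beyond the capsule | No, same reason |
| Obstruction with carcinoma at TURP | Written for a prostate in place |

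One of four is workable.

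**Step 2. Is there a volume for that criterion?** The palpation record is qualitative. In the preliminary series (1.4.6.1), 73.3% of 15 men had lesions, which is 11, and 4 of these had a palpable abnormality (4/11 = 36%). MRI tumor size is kept as a source document (15.4), and 5.4 schedules MRI and/or PET at 3 months, 9 months and 2-2.5 years. But no text links MRI size to the 25% rule, and the footnotes to Appendix I leave the 9-month and 2-2.5-year MRI to the discretion of the principal investigator.

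**Step 3. A man with nodal or bone relapse and PSA below nadir + 2.**

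- Under 9.1 read literally: no clinical or biochemical failure.
- Under 14.5: clinical failure, nodal or distant.
- Under Table 14.5: an event in failure rate and failure-free survival once he starts subsequent therapy. Failure rate also counts prostate cancer death, and failure-free survival counts any death. The 9.1 definition of failure-free survival does not list subsequent therapy, so this back-stop is itself inconsistent between sections.

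The usual error is therefore a late event date. An event is missed altogether if neither therapy nor a counted death follows.

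**Step 4. Who could leave the primary analysis?** All of these must hold: treatment started; radiotherapy not completed or nine-month PSA absent; no biochemical failure and no prostate cancer death in the window; and the only evidence of failure is nodal or distant. The clearest case is metastasis found during treatment. Sections 4.11 and 12.0 stop treatment and remove the man from study, so route (1) is closed. Section 4.11 keeps him in the intent-to-treat analysis, but 14.3 makes the efficacy-evaluable set the main analysis set.

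**Step 5. Size in the primary analysis.** Inputs from 14.2: n = 40, 60% against 80%, one-sided 5%. The exact one-sample binomial reproduces the plan's power, with success at 30 or more of 40:

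- P(X ≥ 30 | 40, 0.60) = 0.0352
- P(X ≥ 30 | 40, 0.80) = 0.8392, which is the stated 83.9%

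Now suppose k of 40 treated men are non-responders who drop out. The documents say only that route (2) is rare, so k is an assumption, treated as fixed. The true rate in all 40 is 60%, the rate among those analysed is 0.60/(1 − k/40), and the critical value is recomputed for n = 40 − k.

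| k | n | Critical value | Rate analysed | One-sided type I error |
|---|---|---|---|---|
| 0 | 40 | 30 | 0.600 | 0.035 |
| 1 | 39 | 29 | 0.615 | 0.067 |
| 2 | 38 | 29 | 0.632 | 0.062 |
| 3 | 37 | 28 | 0.649 | 0.112 |
| 4 | 36 | 27 | 0.667 | 0.190 |

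The dip at k = 2 comes from the discrete critical value.

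Observed results at the boundary, exact test against 60%:

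| Result | One-sided p | Two-sided p |
|---|---|---|
| 29/40 | 0.071 | 0.145 |
| 29/39 (one failure dropped) | 0.045 | 0.073 |
| 30/41 | 0.057 | 0.110 |
| 30/40 (one failure dropped) | 0.035 | 0.054 |

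Dropping one man crosses 5% under the one-sided test of 14.2. It does not under the two-sided tests of 14.5, and the exact 95% interval for 30/40 is 58.8% to 87.3%, which still includes 60%.

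**The case against.** The best defense is that the intent can be read from the plan as a whole. Section 9.0 says relapse is evaluated as defined in what follows, which takes in 9.2.3 and 9.2.4, and points to section 14 for detail. Section 14.5 plainly treats nodal and distant relapse as clinical failure. This stands: the defect is an unreconciled contradiction, not a plan that ignores nodal and distant disease.

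A second defense is that 9.1 does not tie the 25% rule to palpation, and MRI size is recorded. That also stands. The gap is a missing link between rule and measurement, not a total absence of data.

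Two stronger readings are tempting. A reader might infer that metastatic men are generally removed from the primary analysis. They are not: a man with metastasis who completes radiotherapy and has the nine-month PSA stays in through route (1), with his actual PSA. A reader might also take the 4 nodal areas among 17 in the preliminary series as the share of failures that would be missed. Those are areas seen on imaging of men being evaluated for radiotherapy. They are neither relapses after treatment nor counts of men, so they do not measure the defect.

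What the defense does not answer is that 14.3 names 9.1 as the source of endpoint definitions, and 9.1 as worded yields a different classification from 14.5.

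**Conclusion.** The point holds as a contradiction between sections and a definition that does not suit the population. Three of the four criteria in 9.1 do not fit men after prostatectomy, and the fourth has no assigned measure.

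For failure rate and failure-free survival, nodal or distant relapse below nadir + 2 can be missed or dated late, depending on the section followed. Table 14.5 limits this, and the documents give no figure from which its frequency could be estimated.

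For the primary analysis, the exposure is confined to the men described in step 4. The type I error figures depend on the assumed k, on every dropped man being a non-responder, and on the one-sided test of 14.2. They show that the exclusion favors the treatment, not that it will occur. A changed conclusion needs a result at the critical boundary.

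**What to change.** Reconcile the passages into one definition in 9.1:

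1. Clinical failure is the first of local failure, nodal relapse per 9.2.3 or hematogenous relapse per 9.2.4.
2. Remove the criteria that cannot apply after prostatectomy.
3. The sponsor names the measure used for local progression, how it is read, and how missing discretionary scans are handled. Simply writing in MRI volume would not be enough, because later MRI is discretionary and 5.4 allows MRI and/or PET.
4. Use this definition in 14.3 (route 2), 14.5 and Table 14.5, and make the failure-free survival events in 9.1 and Table 14.5 agree on subsequent therapy.
5. State in 14.3 how a man with metastasis found during treatment enters the primary analysis, consistent with 4.11.

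The cost is protocol and SAP wording, settled before outcomes are analysed. The reported failure rate may be slightly higher. No change in sample size follows: with early failures kept as non-responders, the stated design figures stand.

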9.2 Guidelines for Evaluation of Measurable Disease

9.2.1 Clinical primary tumor response will be measured by palpation and recorded in the following ways:

- Pretreatment: A representative drawing of the pretreatment tumor status on DRE, if palpable, will be recorded in the radiotherapy chart.
- Post-treatment: The change in palpable tumor volume will be recorded qualitatively.

9.2.2 PSA levels:

In 98% of patients treated with salvage radiotherapy there is a drop in PSA within 3 months. Those patients that PSA levels have not dropped should be investigated to define the site of progression (local-regional vs. distant metastases). In the rest of the patients, a rising PSA later heralds relapse. Biochemical failure will be modeled after the Nadir+2 definition.[49] Evaluation of patients with a rising PSA profile will include a bone scan, MRI-pelvis/prostate bed, and prostate bed biopsy.

9.2.3 Nodal Relapse

Nodal relapse will be scored as having occurred when appropriate clinical-radiographic evidence(CT or MRI evidence) of this becomes evident (biopsy proof not required in the presence of a rising PSA).

9.2.4 Hematogenous Relapse

Hematogenous relapse will be scored as having occurred when appropriate clinical-radiographic evidence, shows this to be so (biopsy proof not required).

10.0 MEASUREMENT OF TOXICITY

Acute proctitis and cystitis lasting for up to 4 months after completion of radiotherapy are accompaniments of radiotherapy for carcinoma of the prostate. The severity of these reactions is routinely evaluated during treatment and will be scored according to the criteria outlined in Appendix II. In our extensive experience, grade 3 or 4 acute toxicities are rare.

Delayed toxicities are usually related to urinary, rectal, and sexual function. The anticipated urinary and rectal toxicities and severity criteria are those shown in Appendix II. Other untoward clinical events will, however, also be documented.

11.0 ADVERSE EVENT REPORTING

The descriptions and grading scales found in the revised NCI Common Terminology Criteria for Adverse Events (CTCAE) version 4.0 will be utilized for adverse event reporting. A copy of the CTCAE version 4.0 can be downloaded from the CTEP web site (<http://ctep.cancer.gov/reporting/ctc.html>).

11.1 Definitions

11.1.1 Adverse events

Adverse events (AE's) will use the descriptions and grading scales found in the NCI Common Toxicity Criteria in Appendix II.

Adverse events: Any unfavorable and unintended sign (including abnormal laboratory finding), symptom, or disease temporally associated with the use of a medical treatment or procedure, regardless of whether it is considered related to the medical treatment or procedure (attribution of unrelated, unlikely, possible, probable, or definite). Each AE is a unique representation of a specific event used for medical documentation and scientific analysis.

11.1.2 Serious Adverse Events

A **serious adverse event** (SAE) is defined in the FDA CFR 312 as any adverse drug experience occurring at any dose that results in any of the following outcomes: death, a life-threatening adverse drug experience, inpatient hospitalization, or prolongation of existing hospitalization, a persistent or significant disability/incapacity, or a congenital anomaly/birth defect.

SAE's are defined by FDA and therefore seriousness (not severity) serves as a guide for defining regulatory reporting obligations for patient/subject safety. **Serious** is based on patient/event outcome or action criteria usually associated with events that pose a threat to a patient's life or functioning.

The definition of serious adverse event (experience) also includes **important medical events**. Medical and scientific judgment should be exercised in deciding whether reporting is appropriate in other situations, such as important medical events that may not be immediately life-threatening or result in death or hospitalization but may jeopardize the patient or **may require intervention** to prevent one of the other outcomes listed in the definition above. These should also usually be considered serious. Examples of such events are intensive treatment in an emergency room or at home for allergic bronchospasm; blood dyscrasias or convulsions that do not result in hospitalization; or development of drug dependency or drug abuse.

11.1.3 Expected Events

Expected events are those that have been previously identified as resulting from administration of the agent.

11.2 Purpose

Adverse event data collection and reporting, which are required as part of every clinical trial, are done to ensure the safety of patients enrolled in the studies as well as those who will enroll in future studies using similar agents. Adverse events are reported in a routine manner at scheduled times during a trial (please follow directions for routine reporting provided in the Data Reporting Section). Additionally, certain adverse events must be reported in an expedited manner for timelier monitoring of patient safety and care. The following sections provide information about expedited reporting.

Events resulting from concurrent illnesses and reactions to concurrent medications must be reported as adverse events.

Any worsening of the patient's clinical condition while the patient is on study will be considered to be an adverse event unless it is within the normal range of disease fluctuation for that patient.

11.2.1 Determination of Reporting Requirements

Reporting requirements may include the following considerations:

1. Whether the patient has received an investigational or commercial agent;
2. The characteristics of the adverse event including the grade (severity), the relationship to the study therapy (attribution), and the prior experience (expectedness) of the adverse event;
3. The Phase (1, 2, or 3) of the trial; and
4. Whether or not hospitalization or prolongation of hospitalization was associated with the event.

11.2.2 Steps to determine if an adverse event is to be reported in an expedited manner:

- Step 1: *Identify the type of event using the NCI Common Toxicity Criteria (CTC).*

The CTC provides descriptive terminology and a grading scale for each adverse event listed. A copy of the CTC can be downloaded from the CTEP home page (<http://ctep.cancer.gov>). Additionally, if assistance is needed, the NCI has an Index to the CTC that provides help for classifying and locating terms. All appropriate treatment locations should have access to a copy of the CTC.

- Step 2: *Grade the event using the NCI CTC.*
- Step 3: *Determine whether the adverse event is related to the protocol therapy (investigational or commercial).* Attribution categories are as follows: Unrelated, Unlikely, Possible, Probable, and Definite.
- Step 4: *Determine the prior experience of the adverse event.*

11.3 Reporting Methods

11.3.1 FDA Reporting

N/A

11.3.2 IRB Reporting

Report of AEs and SAEs must be reported according to UM IRB policy and procedures.

11.3.3 Follow-up Reporting

For all SAE's, the investigator is obligated to pursue and provide follow-up reporting information until the event has resolved or until an acceptable medical endpoint has been reached or the patient is lost to follow-up.

